6.5 Vital Signs

Blood pressure and pulse will be recorded after at least 5-minute rest in the sitting position. Two measurements should be made for each blood pressure measurement and the average recorded. Vital sign checks will be performed according to the schedule summarized in Appendix 3.

6.6 Electrocardiogram

All ECGs will be obtained in the decubitus position following a 10-minute rest time.

All ECG recordings must be performed using a standard high-quality, high-fidelity electrocardiograph machine equipped with computer-based interval measurements. Digital ECG recording is recommended.

For safety monitoring purposes, the investigator or physician delegate must review, sign and date all ECG tracings. Paper copies will be kept at the study center with the subject's clinical file as part of the permanent record. The ECG intervals and interpretation will be recorded on the eCRF.

The following parameters PQ (PR), QRS, QT and QTcB (calculated according to Bazett's formula) and the heart rate will be measured automatically and recorded in the eCRF. In addition, any observed abnormality will be reported and documented.

6.7 Laboratory Analyses

A full clinical laboratory profile including hematology, biochemistry, lipids and other analyses will be performed during the study as outlined in Appendix 3.

All lab tests are performed in the 10-hour fasting state (water allowed). If a subject has not adhered to the 10-hour fast, the visit can be rescheduled within approximately 1-3 days (maximum visit window is +/- 5-days). Urine samples will be analysed and destroyed. Blood samples will be retained during the study and for up to 6 months following completion of the trial to facilitate complete analysis and for the potential analysis of additional lipid, or lipoprotein or biomarker analyses.

6.8 Concomitant and Prohibited Medications

The investigator or designee will review the concomitant medications being taken by the subject. Any AE that leads to the administration of any new concomitant medications will be reported as an AE.

The use of medications or supplements which may have a possibility of altering lipid levels (see Exclusion #1 and #2) should be avoided until after end of treatment or ideally, study completion at Week 14. Oral or parenteral hormonal contraceptive agents should be stabilized prior to study entry and maintained stable throughout the course of the trial. Use of NSAIDs is prohibited with the exception of acetylsalicylic acid (ASA) at a concentration of up to 325 mg twice a day and occasional/intermittent use for the symptomatic control of minor acute ailments (e.g. headaches).

In the course of the study, patients will be receiving standard medical care at the discretion of the treating physician. During the treatment period, the investigators will carefully monitor and consider adjusting the dose in patients who are taking concomitant medications known to have hypotensive properties such as immunosuppressants, antihypertensive drugs or natural health products (e.g. andrographis, casein peptides, cat's claw, coenzyme Q-10, fish oil, L-arginine, lyceum, stinging nettle, theanine).

6.9 Adverse Events

Adverse events (serious and non-serious) will be collected throughout the study from randomization to last dose of IP taken. SAEs will be collected from the time of consent through to 2 weeks after the last dose of study product. At each visit, the investigator or designated qualified study site staff will ask the subject if any untoward medical event occurred since the last visit. For each event, the date of onset and end, severity, relationship to IP, outcome and treatments administered for the event will be recorded in the eCRF.

6.10 Unscheduled Visit

All attempts should be made to keep subjects on the study schedule. Unscheduled visits may be necessary to repeat testing following abnormal laboratory results, for follow-up of AEs, or for any other reason, as warranted.

The following information will be collected at any unscheduled visit:

- New/change in concomitant medications
- AEs

Details of these visits will be recorded as appropriate.

6.11 Early Termination Visit

Any subject terminating from the study early during the treatment period will, at the time of withdrawal, be encouraged to complete all Visit 4 (Week 12) procedures if possible.

6.12 Efficacy Assessments

6.12.1 Primary Efficacy Assessment

The primary efficacy assessment is direct-measured of LDL-cholesterol.

6.12.2 Secondary Efficacy Assessment

The secondary efficacy assessments include TC, non-HDL-C, small LDL subclass particle concentration, hsCRP, apo B, and VLDL-C.

6.13 Exploratory Assessments

Exploratory assessments include HDL-C, TG, Lp(a) and HbA1c.

6.14 Safety Assessments

Safety will be assessed by adverse events, physical examination, ECG, vital signs, and laboratory analyses (hematology and biochemistry).

6.15 End of Study

The end of the study is defined as the date of the last visit of the last subject. Last visit of the last subject is either the date of the last visit of the last participant to complete the study, or the date at which the last data point from the last subject, which was required for statistical analysis (i.e. key safety and efficacy results for decision making), was received, whichever is the later date.

6.16 Dietary and Concomitant Medications Restrictions

At the screening visit subjects should be already on a standard cholesterol lowering diet and they should maintain it throughout the study. Subjects are encouraged to pursue a healthy lifestyle. The subjects must abstain from/minimize alcohol (EtOH) intake and control any other variables that may alter serum lipid levels (e.g., strenuous exercise, weight loss programs, drugs including over the counter preparations that may alter serum lipid levels).

7 ADVERSE EVENTS (AE) AND SERIOUS ADVERSE EVENTS (SAE) / SAFETY INSTRUCTIONS AND GUIDANCE

The investigator is responsible for the detection and documentation of events meeting the criteria and definition of an adverse event (AE) or a serious adverse event (SAE) as provided

in this protocol. During the study, when there is a safety evaluation, the investigator or site staff will be responsible for detecting AEs and SAEs, as detailed in this section of the protocol.

7.1 Definition of Adverse Event (AE)

As per Natural Health Products Regulations SOR/2003-196, an AE is any adverse occurrence in the health of a clinical trial subject who is administered a natural health product that may or may not be caused by the administration of the natural health product, and includes an adverse reaction, a serious adverse reaction and a serious unexpected adverse reaction.

Exacerbation of a chronic or intermittent pre-existing condition including either an increase in frequency and/or intensity of the condition is to be reported as AE. Signs, symptoms, or the clinical sequelae of a suspected overdose of either IP or a concurrent medication are to be reported as AEs.

Medical or surgical procedures (e.g. endoscopy, appendectomy) are not to be reported as AEs; the medical condition that leads to the procedure is an AE.

7.2 Definition of Serious Adverse Event

A serious adverse event is a noxious and unintended response to a natural health product that occurs at any dose and that requires in-patient hospitalization or prolongation of existing hospitalization that causes congenital malformation, results in persistent or significant disability or incapacity, is life-threatening or results in death.

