6.1 Screening Assessments

All subjects must provide written informed consent before any study-specific assessments or procedures are performed including 10-hour fasting for labs.

Screening procedures (Visit 1, up to 7 days prior to Baseline Visit 2) to assess eligibility include medical history, height, weight, physical examination, vital signs, ECG, concomitant medications, and lab blood draw per Appendix 3.

Urine pregnancy test is performed in females of childbearing potential.

Subjects who fail to meet inclusion/exclusion criteria may not be re-screened for study entry.

Subjects taking supplements defined in the exclusion criterion #2 and who accept to stop taking these supplements, may be randomized after a 30-day wash out period. If during the screening period it is determined that a subject is taking an excluded supplement, it is permissible to extend the 7-day screening period to allow for a 30-day washout in these exceptional circumstances.

Any clinically significant AE occurring prior to subject randomization is to be reported in the Medical History, and if serious, should be recorded as a SAE.

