7.4 Time Period, Frequency, and Method of Detecting AEs and SAEs

All serious adverse events (SAEs) will be captured from the time of consent through to week 14 safety Follow up phone call. All AEs will be captured between the time of randomization up to the last dose IP taken. Each study participant will be monitored by the investigator and study staff for AEs/SAEs occurring throughout the study. The investigator or designee will enquire about AEs/SAEs in a non-specific manner through the study at all visits.

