7.7 Expeditable Events (SUSAR's)

During the course of a clinical trial, the sponsor / or delegate shall notify the regulatory authorities of any serious unexpected adverse reaction to the natural health product that has occurred inside or outside Canada as follows:

- a) if it is neither fatal nor life threatening, the regulatory authorities should be notified immediately if possible, and no later 15 days after the sponsor becomes aware of the information; and
- b) if it is fatal or life threatening, the regulatory authorities should be notified immediately if possible and no later than seven days after the sponsor becomes aware of the information.

c) Within eight days after having informed the regulatory authorities of a serious unexpected adverse reaction to the natural health product, the sponsor must submit a report as complete as possible that includes an assessment of the importance and implication of any findings. The final report should include relevant previous experience with the same or similar health products.

A serious adverse reaction is a serious adverse event that is **CAUSALLY** related to the investigational product.

Serious expected adverse reactions could qualify for an expedited reporting if there is a clinically significant increase in the rate of its occurrence within the study population. Appropriate scientific and medical judgment should be applied.

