1 INTRODUCTION

The purpose of this statistical analysis plan (SAP) is to present the statistical methodology that will be used for the final analysis of CEAPRO Inc. protocol PROJ1601. This plan also provides a description of the tables, figures and listings that will be included in the final statistical report. It is based on the protocol version 2.1 dated 23JAN2020 and on the annotated case report form (CRF) version 2.0. In case of differences in terms of descriptions or explanations between the SAP and the clinical protocol, the SAP will supersede the protocol. Any deviation to this SAP would be reported in the statistical report.

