5.2 Serious Adverse Events

A serious adverse event is a noxious and unintended response to a natural health product that occurs at any dose and that requires in-patient hospitalization or prolongation of existing hospitalization that causes congenital malformation, results in persistent or significant disability or incapacity, is life-threatening or results in death.

SAEs will be collected from the time of consent through to 2 weeks after the last dose of study product.

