9 APPENDICES

9.1 Appendix 1 - Schedule of visits

| Procedure/Visit | Screening Period (V1) | Randomization Baseline Visit (V2) | Visit 3 (V3) | End of Treatment Visit (V4) | Safety Follow-up Visit (V5) (telephone) |
|---|--------------------------|---|----------------------|-----------------------------------|--|
| | Week -1 Up to 7 days | Week 0 | Week 6 (± 5 days) | Week 12 (± 5 days) | Week 14 (± 5 days) |
| Informed consent form | X | | | | |
| Inclusion & Exclusion criteria | X | X | | | |
| Medical History | X | X | | | |
| Demographics | X | | | | |
| Physical examination | X | | | X | |
| Vital signs (blood pressure, pulse) | X | X | X | X | |
| Height | X | | | | |
| Weight | X | | | X | |
| Dietary counselling including alcohol consumption, and timing of statin vs. IP intake | X | X | X | | |
| Check compliance on statin and IP | | | X | X | |
| 12-Lead ECG | X | | | X | |
| Hematology | X | X | X | X | |
| AST, ALT, Creatinine | X | X | X | X | |
| Bilirubin | X | | | | |
| LDH, CPK | | X | X | X | |
| TG, TC, LDL-C, HDL-C | X | X | X | X | |
| LDL-C (direct-measured), VLDL-C, apo-B, Lp(a), non-HDL-C, small low-density lipoprotein (LDL) subclass particle concentration | | X | X | X | |
| HbA1c, Insulin, Glucose and hsCRP | | X | | X | |
| Concomitant medication | X | X | X | X | |
| Pregnancy test* | X* | X* | | | |
| Randomization | | X | | | |
| IP dispensing | | X | X | | |
| Adverse Events | X** | X** | X** | X** | X** |

*Female patients of childbearing potential will have a urine pregnancy test performed at the screening visit and at randomization (visit 2)

**Serious Adverse Events (SAEs) are captured from the time of consent through to week 14 safety Follow up phone call. AEs are captured between the time of randomization up to the last dose IP taken.

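### The SAE definition builds in causality and contradicts the rules around it, the two causality categories leave a gap, and the safety call that closes SAE collection has two anchors

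*Protocol*

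**What the plan says.** **Definition.** Protocol 7.2 and SAP 5.2 carry the same sentence: "A serious adverse event is a noxious and unintended response to a natural health product that occurs at any dose", followed by the list of qualifying outcomes. The AE definition in Protocol 7.1 is neutral on causality.

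**Other uses of the term SAE.** Protocol 6.1 covers events before randomization "and if serious, should be recorded as a SAE". Protocol 7.4 states: "All serious adverse events (SAEs) will be captured from the time of consent through to week 14 safety Follow up phone call". Protocol 7.7 says that "A serious adverse reaction is a serious adverse event that is" causally related to the product. Protocol 7.8.2 requires a relationship judgement for every AE and SAE, with Related and Not Related as the only options.

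**Windows.** For AEs, Protocol 7.4 says: "All AEs will be captured between the time of randomization up to the last dose IP taken". For SAEs, SAP 5.2 says: "SAEs will be collected from the time of consent through to 2 weeks after the last dose of study product", as does Protocol 6.9. The footnote in SAP Appendix 1 says: "Serious Adverse Events (SAEs) are captured from the time of consent through to week 14 safety Follow up phone call", in line with Protocol 7.4 and the footnote in Protocol Appendix 2. SAP 1 provides that where the documents differ, "the SAP will supersede the protocol".

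**The concern.** The safety profile is a secondary objective and there is no DSMB, so the trial relies on investigators applying these definitions. The 7.2 wording is operative. The opening of Protocol 7 makes investigators responsible for detecting events that meet the protocol's definitions, and 7.3 refers to 7.2 when deciding whether an abnormal finding is an SAE. An investigator who takes 7.2 at its word would not complete an SAE form for a serious event thought unrelated.

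The causality rating feeds the count of subjects with a related TEAE (SAP 6.5.2.1). It also decides whether a serious event is a reaction for expedited reporting under 7.7. If the threshold is unclear, sites may apply it differently.

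The closing date for SAEs matters most for subjects who stop product early but stay in follow-up, as Protocol 4.3 allows.

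**Working it through.** The plan states no figure on this point. The first two checks compare text; the third needs simple day arithmetic.

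**1. Definition against use**
- 6.1 and 7.4 record SAEs before any product is taken. Such an event cannot be a response to the product.
- 7.7 separates a reaction from an SAE by causality. If every SAE were already a response, the distinction would be empty.
- 7.8.2 allows an SAE to be Not Related. Under 7.2 no such SAE could exist.
- 7.8.1 calls an event serious when it meets one of the outcomes in 7.2. This points to an outcome-based intent, which 7.2 itself does not state.

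Consequence of the literal reading, by time of onset:
- *Consent to randomization:* 6.1 still sends clinically significant events to the medical history. Tables 3.2.3 and 3.2.4 are treatment-emergent, so only recording and listing are affected.
- *Randomization to last dose:* an unrelated serious event is still an AE under 7.1 and, if treatment-emergent, is counted in Tables 3.2.1 and 3.2.2. It loses the serious label, the 24-hour report under 7.6, and its place in Tables 3.2.3 and 3.2.4.
- *After last dose:* AE collection under 7.4 has ended, so an event that is not called an SAE has no clear route into the data.

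**2. Causality categories in 7.8.2**
- Not Related requires a definitive alternative cause that the clinician has documented.
- Related requires clear evidence of causation, with other contributing factors excluded.
- An event with plausible timing and a possible but unproven alternative cause meets neither description, and no default is given.

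**3. Timing of the safety call and the SAE end point**
- The call is placed 2 weeks after last dose in the synopsis (duration of treatment), 5.1.7, 6.2 and SAP 2.1.
- It is placed at Week 14 in 3.1, 6.2, SAP 2.1 and both visit schedules. Sections 6.2 and SAP 2.1 therefore contain both anchors.
- Inputs: Week 12 = Day 84 (SAP Appendix 2); Week 14 = 84 + 14 = Day 98; call window ±5 days.
- With last dose on day d, the end point in 6.9 and SAP 5.2 is d + 14. The end point in 7.4 and the footnotes is the day of the call.
- *Call follows last dose:* the call falls on d + 14 and the difference is 0.
- *Call stays at Week 14:* the difference is 98 − (d + 14) = 84 − d, before the ±5-day window.
  - Completer, d = 84: 84 − 84 = 0 days.
  - Stops at the Week 6 visit and stays, d = 42: Day 56 against Day 98, or 42 days (37 to 47 with the window).

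Two smaller faults sit beside this. The first sentence of 6.9 ends collection of both serious and non-serious events at last dose, while its next sentence carries SAEs 2 weeks further. Section 6.2 also describes the call as being for any AEs, although AE collection ends at last dose.

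**The case against.** The strongest defence is that the intent can be recovered. Section 7.8.1 reads seriousness from outcomes, 7.4 asks for all SAEs from consent, and 7.6 asks for a causality assessment with every initial SAE report. A trained investigator would probably report unrelated serious events. That is fair and limits the likely damage, but the definition itself still says otherwise and the SAP repeats it.

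Several stronger readings are tempting, and the documents do not support them:
- *Unrelated serious events would vanish from the safety data.* Between randomization and last dose they remain AEs under 7.1. Expedited reporting under 7.7 concerns reactions only, so the narrow definition does not remove events from it.
- *The related-TEAE count is undefined.* Section 7.8.2 tells investigators to use clinical judgment, so a rating will exist. What is ambiguous is the threshold. The phrase in 5.2 about causality that cannot be excluded is a condition for unblinding, not a competing rating scale.
- *The SAP flatly contradicts itself on the SAE window.* SAP 2.1 also ties the call to last dose, and on that reading SAP 5.2 and the Appendix 1 footnote give the same end point. The defect is the double anchor. Because both anchors appear in the SAP, its precedence over the protocol does not choose between them.
- *Section 6.2 opens a second AE window.* The call can collect late reports of events that began before last dose, and 7.2.1 has ongoing events reviewed at later contacts. The wording is loose at most.

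**Conclusion.** The SAE definition is wrong as written and should be corrected. It cannot be reconciled with 6.1, 7.4, 7.7 and 7.8.2. If followed literally, it removes serious events judged unrelated from the 24-hour report and from the two serious-event tables. The causality gap and the double anchor are real but narrower: one leaves a threshold ambiguous, the other leaves an end date open.

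The 84 − d figure assumes that the call is held at Week 14 independently of last dose and that the subject stops product early and remains in the study. It counts calendar days, not events lost. The documents give no event rates and no expected number of early stoppers who stay, so the number of affected events cannot be computed. Safety analysis is descriptive, the same rules apply to active and placebo within each tier, and no efficacy result changes.

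**What to change.** (a) In Protocol 7.2 and SAP 5.2, define an SAE as any adverse occurrence that meets one of the outcomes already listed, regardless of causality. Keep the response-based wording for the serious adverse reaction in 7.7, and check the text against the regulation cited in 7.6.

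(b) Make 7.8.2 exhaustive by defining one category as the complement of the other. Both texts need rewriting. If Related becomes the default, its demand for clear evidence must go; if Not Related does, its demand for a documented definitive cause must go. The first choice raises the related count and the second lowers it, so fix the choice before unblinding.

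(c) Choose one anchor for the safety call, and state how it applies to subjects who stop product early and stay. Reconcile the AE and SAE windows to it in the synopsis, Protocol 3.1, 5.1.7, 6.2, 6.9, 7.4 and Appendix 2, and in SAP 2.1, 5.2 and Appendix 1. As a minor addition, align the TEAE period in SAP 5.1 and 6.5.2.1 with the chosen AE window, since it has no end date now.

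The cost is wording in the protocol, eCRF guidance and SAP, with no new visit and somewhat more event reporting. SAP 6.1 describes randomization in the past tense. A change made after enrolment began will not recover events that were never recorded, and reporting may differ between the sequential dose tiers. In that case, report the date of the change and apply the same summary rules to all tiers.

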7.2.1 Follow-up of AEs/SAEs

After the initial AE/SAE report, the investigator is required to proactively follow each study participant and provide further information on the study participant's condition.

All AEs/SAEs documented at a previous visit or contact and designated as ongoing, will be reviewed at subsequent visit or contacts. All AEs/SAEs will be followed until resolution, until the condition stabilises, until the event is otherwise explained, or until the study participant is lost to follow-up.

The appropriate AE/SAE eCRF page(s) will be completed and updated with follow-up information. Follow-up will include any supplemental investigations carried out to elucidate the nature and /or causality of the AE or SAE. This may include additional laboratory tests or investigations, histopathological investigations, or consultation with other health care physicians.

7.3 Laboratory Test Abnormalities and other abnormal assessments as AEs or SAEs

Abnormal laboratory findings (e.g. clinical biochemistry, hematology) or other abnormal assessments (e.g. ECG, vital signs) that are judged by the investigator as clinically significant will be recorded as AEs or SAEs if they meet the definition of an AE, as defined in Section 7.1, or SAE as defined in Section 7.2.

Clinically significant abnormal laboratory findings or other abnormal assessments that are detected during the study or are present at baseline and significantly worsen following the start of the study will be reported as AEs or SAEs. However, clinically significant abnormal laboratory findings or other abnormal assessments that are associated with a disease reported in the medical history, unless judged by the investigator as more severe than expected for the participant's condition, or that are present or detected at the start of the study and do not worsen, will not be reported as AEs or SAEs.

Any treatment-emergent abnormal laboratory result which is clinically significant, i.e., meeting one or more of the following conditions, should be recorded as a single diagnosis on the AE page in the eCRF:

- Accompanied by clinical symptoms
- Leading to a change in IP (permanent or temporary discontinuation)
- Requiring a change in concomitant therapy (e.g. addition of, interruption of, discontinuation of, or any other change in a concomitant medication, therapy or treatment).

This applies to any protocol and non-protocol specified safety and efficacy laboratory result from tests performed after the first dose of IP, which falls outside the laboratory reference range and meets the clinical significance criteria.

This does not apply to any abnormal laboratory result which falls outside the laboratory reference range but which does not meet the clinical significance criteria (which will be analysed and reported as laboratory abnormalities) or those which are a result of an AE which has already been reported.

